6.0 STUDY TREATMENT

STUDY DRUG

6.1 Atorvastatin

Metabolism and mechanism of action

Atorvastatin calcium belongs to a group of lipid lowering agents referred to as statins. Atorvastatin is a selective competitive inhibitor of the enzyme 3 hydroxy-3methylglutaryl coenzyme A (HMG CoA reductase). This enzyme catalyzes the conversion of HMG CoA to mevalonic acid, the rate- limiting step in cholesterol biosynthesis. This class of drugs have been utilized in both the primary and the secondary prevention of coronary artery disease (CAD) [34] [35] [36].

Atorvastatin is orally administered and is well tolerated. Atorvastatin is metabolized by the cytochrome P450 3A4 system to ortho and para hydroxylated metabolites. Atorvastatin and its metabolites are primarily hepatically excreted [37]. The metabolism of atorvastatin may be influenced by CYP 3A4 inducers and inhibitors.

Adverse effects of Atorvastatin

The most common side effects associated with atorvastatin use are gastrointestinal. In clinical trials the following events were reported as per the package insert in greater than 2% of the cases: chest pain, nausea, bronchitis, rhinitis, arthritis, insomnia and dizziness, urinary tract infection and peripheral edema.

Atorvastatin and effects on liver enzymes

Persistent elevations in liver enzyme to 3 times the ULN have been reported in 0.2-2.3% of patients studied on clinical trials of atorvastatin. Upon discontinuation of the drug these elevations are reversible. Fatal liver injury has been reported with atorvastatin use [38]. Overall it appears that fatal liver injury is a rare event in patients using statins. Liver function abnormalities associated with atorvastatin use are seen at all doses. However, the incidence of these abnormalities is greater with higher doses of the drug.

In a recently reported study of secondary prevention of CAD, 10,001 patients were randomized to receive either 10 or 80 mg of atorvastatin. In this study persistent elevation in liver enzymes were seen in less than 1% of all patients, however the incidence was significantly higher in the 80 mg subgroup (1.2% vs 0.2%). [39]

The package insert states that the use of atorvastatin is not recommended in patients with active liver disease. Serial monitoring of liver function tests prior to start of drug, 6 to 12 weeks after and semi annually thereafter is advised by the drug manufacturers. More stringent monitoring at shorter intervals will be done as part of this protocol.

Atorvastatin and myopathy

Myalgia and rhabdomyolysis have been reported with atorvastatin use. In the ASCOT study there was a single case of non-fatal rhabdomyolysis among 5168 patients randomized to atorvastatin. [40] In a study of secondary prevention of CAD, among 10,000 patients randomized to receive either 10 or 80 mg of atorvastatin there were 5 cases of rhabdomyolysis.[39] While rhabdomyolysis is a complication of atorvastatin it appears relatively rare.

The risk of myopathy is increased when atorvastatin is used in conjunction with azole antifungals, erythromycin, clarithromycin, niacin, fibric acid derivatives or cyclosporine [37]. Patients who use fibric acid derivatives, niacin and cyclosporine will not be enrolled into the

study. Patients who start azoles or erythromycin or clarithromycin while on study will be monitored closely for signs and symptoms of myopathy, patients on these drugs at the time of enrollment will not be eligible for this study until completion of therapy with these agents.

In addition the risk of myopathy is increased with the concomitant use of grape fruit juice and atorvastatin. These interactions are mediated via the cytochrome p 450 system; grape fruit juice is an inhibitor of this system [41] While on study patient will be advised to avoid grape fruit juice and grape fruit.

To reduce risk to our study patients we will monitor liver function (LFT) and creatinine phosphokinase (CPK) at baseline and as indicated in the schedule of events. Patients will also be questioned about myalgia or weakness at each visit. Presence of any of these symptoms will require complete evaluation as judged suitable by their health care provider. Patients who participate in this study will be asked to refrain from vigorous exercise regimens for the study period. Vigorous exercise is known to increase CPK levels and may cause patients to be unnecessarily excluded /withdrawn from the study.

- Pregnancy and breast feeding are contraindications for atorvastatin use; atorvastatin is classified as a pregnancy category X drug. Pregnant or nursing women will not be enrolled in this study and patients will be required to use reliable methods of contraception to be enrolled in this study. If a patient becomes pregnant on study, she will be asked to stop taking study drug and will be followed through her pregnancy and the peripartum period.

6.2 Product Supply, Distribution, and Pharmacy

Both drugs (i.e. atorvastatin and Placebo) will be formulated by the NIH PDS and will be supplied to both the sites. Both placebo and drug will be identical in appearance. They will be packaged and labeled with the study number, and will have a space where the subjects initial and randomization number will be entered.

6.3 Drug Storage

Both drugs and placebo can be stored at room temperature in a locked storage area.

6.4 Accountability of drugs

Some drug records will be maintained centrally by the NIH PDS such as shipping records. The individual sites will also maintain drug records locally such as drug dispensing and

accountability records. Drugs will be dispensed to the sites by NIH PDS. Patients will be required to pick up medications per visit schedule.

7.0 STATISTICAL CONSIDERATION

This is a double blind randomized crossover placebo controlled trial of statin use in HIV positive patients with the specific aim of studying the effect of statins on HIV viral load. 22 chronically infected HIV positive patients will be randomized to either atorvastatin 80 mg followed by placebo or placebo followed by atorvastatin (11 per sequence). After 8 weeks of treatment and another 4 weeks washout period, patients in the placebo arm will receive atorvastatin 80mg, whereas patients in the atorvastatin arm will be followed on placebo for another 8 weeks. Table 2 displays the treatment sequence for the two groups.

(Week 0-7)	Week 8-11	(Week 12-19)
Atorvastatin 80mg	Washout	Placebo
Placebo	Washout	Atorvastatin 80mg

Table 2

The effect of lipid lowering agents on HIV-1 RNA levels will be evaluated at the end of 7 weeks and at the end of 19 weeks. The primary goal of this study is to assess the treatment effect by assuming that the carry-over effect is negligible. The primary strength of this cross-over trial is increased efficiency because each patient serves as his or her own control, and the within-subject variability is usually less than the between-subject variability. As a result, the sample size for a cross-over trial will be lower than that for a comparable parallel group design. There is a possible drawback of this design, however, if the carry-over effect cannot be ignored.

Based on historical data we estimate the standard deviation of the log₁₀ viral load as .74 and the correlation coefficient of log₁₀ viral loads before and after treatment as 0.83. To be conservative, a correlation coefficient of 0.75 is used in our calculation. The paired t-test is used

for power calculation. A trial of 20 subjects has a power of 77% (with type I error 0.05) for detecting a 1/3 log₁₀ drop in viral load with atorvastatin. Power to detect a change of 0.4 or 0.5 in log₁₀ viral load based on 10 patients per sequence is 90% and 98% respectively. Thus we have excellent power to detect at least .4 log₁₀ viral load difference by the treatment and reasonable power to detect a 1/3 log₁₀ viral load difference. Due to the possible loss to follow-up (10%), 11 patients will be accrued in each sequence.

At the end of this study, the paired t-test will be used to test this hypothesis. If the underlying distribution is clearly not close to a normal, then the sign-rank Wilcoxon test will be used instead.

Secondary Objectives for Statistical Consideration

1- To study the difference in the expression of immune activation markers (i.e HLA DR CD38 and Ki67 expression both percentage and number on CD4+ and CD8+ cells) between the end of 7 weeks and the end of 19 weeks in the placebo and atorvastatin sequence. All comparisons of changes between the end of 7 weeks and the end of 19 weeks, i.e. the difference between months 19 and 7 or months 7 and 19 will be conducted by using the paired t-test if the measurements are continuous. McNemar statistic will be used for the changes of discrete markers.

Because of the randomization, the baseline measurements (at beginning of this trial) in placebo and atorvastatin sequences should have the same distribution. This information can be incorporated into an additional statistical analysis, called analysis of covariance ANCOVA. A linear mixed effects model can be used to analyze the difference between the change of viral loads evaluated at the beginning of this trial and at the end of the 7th week, and at the end of 11th week and 19th week in atorvastatin and placebo sequence and placebo and atorvastatin sequence. The difference of viral load at the end of 11th week in two treatment sequences can be used to assess whether there is a treatment carryover effect.

Additional analyses will be conducted to assess whether there is any effect of drug on change viral load, beyond that predicted by the change in LDL.

Finally the correlation between reductions in serum cholesterol and HIV viral load in treatment arm will be assessed by using Spearman's correlation coefficient statistics.

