3.0 OBJECTIVES

3.1 Primary objective

The primary objective of this study is to compare the changes in HIV-1 viral load during the atorvastatin phase with the changes in viral load in the placebo phase.

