5.3.1 Prerandomization evaluations

After signing either the screening/study informed consent, patients will undergo screening tests. Screening will include a complete medical history and physical examination. Laboratory testing will include a fasting lipid profile, flow studies (FACS), routine safety labs which will include a liver function test and creatinine kinase assay, a hepatitis profile and viral load assay to establish baseline viral load. Due to the variability in the viral load assay, we will utilize a minimum of 3 viral load assays to establish a baseline. All testing will need to be completed within a 4 week period prior to randomization. During this period, patients may come in for testing at their own convenience, but testing will not be done more than once within a 24 hour period. All laboratory tests except standard safety labs will be done centrally at SAIC Frederick to maintain consistency. Volunteers at the NIH who satisfy the inclusion criteria and who continue to be interested in the protocol will be now required to sign the study consent.

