5.3.4 On study evaluations

Efficacy Assessments

Patients will undergo HIV BDNA assays on days 7, 14, 42, 56, 84, 91, 98, 126, 140 and 168. Patients will also undergo evaluation for immune activation markers levels specifically CD38 and HLA-DR expression on CD4 and CD8 cells and Ki67 will be done on days 7, 56, 84, 91, 140 and 168. Fasting lipids, apolipoprotein and ultrasensitive hsCRP will be done at randomization and on day 7, 56, 84, 91, 140 and 168. All testing other than standard safety testing will be done at SAIC Frederick. The Beck depression inventory and the Piper fatigue scale will be administered on days 56, 84, 140 and 168.

Safety assessments

Safety assessments will be done at specified study visits and will include clinical assessment, physical exam, medication assessment, routine chemistry and hematology, serum creatinine phosphokinase, liver function tests, and serum pregnancy tests. The Piper Fatigue Scale will be administered prior to and following each arm. Please see table 1 for details. All safety labs will be done at the individual institutions. All laboratories performing study related tests are CLIA certified laboratories

Genetic studies

TSG 101 genotyping and HLA typing will be performed. Additional genotyping of specific host genes will be performed as indicated. Additional blood will be obtained as indicated for storage and future use.

Adherence assessment

Pill counts will be performed at each visit to monitor adherence to the protocol, and patients will be asked about adherence.

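### The primary comparison uses one viral load per period, although a matched on-treatment load two weeks earlier is already drawn in each period and enters no named analysis

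*Combined protocol and SAP*

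**What the plan says.** Section 7.0 states that the effect on HIV-1 RNA "will be evaluated at the end of 7 weeks and at the end of 19 weeks" and tests it with a paired t-test, or a signed-rank test if the data are clearly non-normal. Table 2 numbers the treatment periods as weeks 0-7 and 12-19, so the two evaluation times are D56 and D140.

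The power calculation takes the "standard deviation of the log₁₀ viral load as .74" and says that "a correlation coefficient of 0.75 is used in our calculation"; the historical estimate was 0.83. It concludes: "A trial of 20 subjects has a power of 77% (with type I error 0.05) for detecting a 1/3" log10 drop.

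Section 5.3.4 schedules "HIV BDNA assays on days 7, 14, 42, 56, 84, 91, 98, 126, 140 and 168", and Table 1 agrees. D42 and D126 each fall 14 days before the evaluation visit, on study treatment, at the same point of their period. The additional mixed model described under the secondary objectives uses only the start of the trial and the ends of weeks 7, 11 and 19.

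For baseline, section 5.3.1 says: "Due to the variability in the viral load assay, we will utilize a minimum of 3 viral load assays to establish a baseline".

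Section 3.1 words the primary objective as to "compare the changes in HIV-1 viral load during the atorvastatin phase with the changes in viral load in the placebo phase".

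**The concern.** The protocol replicates the viral load at baseline because the assay varies, but the value that decides the trial is a single load in each period. The same short-term assay and biological noise affects that load. A second load under the same treatment has already been paid for and drawn, and the plan leaves it out.

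With about 20 evaluable patients and planned power of 77% for the smallest effect of interest, precision matters. There is also a practical exposure: with one value per period, a missed or failed assay on D56 or D140 removes the patient from the paired test, and section 7.0 gives no fallback.

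**Working it through.** **Inputs from section 7.0.** SD of one log10 load σ = 0.74; correlation between the paired loads r_b = 0.75; n = 20; type I error 0.05 (sidedness not stated; two-sided reproduces the figures); effect 1/3 log10.

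**Step 1: reproduce the plan.** SD of the paired difference = σ√(2(1 − r_b)) = 0.74 × √0.5 = 0.523. Noncentrality = (1/3) × √20 / 0.523 = 2.85 on 19 df. Power from the noncentral t is 77.1% for 1/3 log10, 90.0% for 0.4 and 98.2% for 0.5. The plan states 77%, 90% and 98%, so its figures are right for its inputs.

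Two reference values: with r_b = 0.83 the SD is 0.431 and power for 1/3 log10 is 90.6%. With r_b = 0.75 and all 22 patients evaluable, power is 81.3%.

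**Step 2: average two loads per period.** Let r_s be the correlation between the two loads of one period, and let every cross-period pair have correlation 0.75. Then

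Var(difference of means) = 2σ²[(1 + r_s)/2 − r_b] = 1.0952 × [(1 + r_s)/2 − 0.75].

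For example, r_s = 0.90 gives 1.0952 × 0.20 = 0.219, so the SD is 0.468.

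The documents do not give r_s. The value 0.75 is the most favourable case, because it makes loads 14 days apart on one treatment no more alike than loads 12 weeks apart on different treatments.

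**Step 3: allow for a smaller effect at week 6.** If the week-6 effect is a fraction f of the week-8 effect, the averaged effect is (1/3)(1 + f)/2. A 5% dilution means f = 0.90; a 10% dilution means f = 0.80.

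Power for 1/3 log10 at n = 20, against 77.1% with one load per period:

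| Assumed r_s | SD of difference | No dilution | 5% dilution | 10% dilution |
|---|---|---|---|---|
| 0.75 | 0.370 | 96.8% | 95.2% | 93.0% |
| 0.83 | 0.425 | 91.4% | 88.5% | 84.9% |
| 0.90 | 0.468 | 85.6% | 81.9% | 77.6% |
| 0.95 | 0.496 | 81.3% | 77.2% | 72.7% |
| 0.98 | 0.513 | 78.8% | 74.6% | 70.0% |

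Averaging breaks even when the dilution equals 1 − (SD of averaged difference)/0.523. That is 29%, 19%, 11%, 5% and 2% down the rows.

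**Step 4: if the endpoint is a difference of changes.** The wording of section 3.1 allows this reading, and the table then does not apply. As an illustration, assume a correlation of 0.75 between all four loads (start and end of each period). The variance is 4σ²(1 − 0.75) = σ², so the SD is 0.74 and power for 1/3 log10 is about 48%. Averaging only the on-treatment loads gives about 60% if r_s = 0.75 and about 51% if r_s = 0.94.

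**The case against.** A single end-of-treatment value is a legitimate prespecified choice. It measures the effect at the longest exposure and avoids dilution, and the documents give no time course for an antiviral effect of atorvastatin. The stated power is correct and rests on a deliberately low correlation, and section 7.0 openly ranks its power for 1/3 log10 below its power for 0.4. The size of any gain depends on a correlation that nobody has supplied. All of this stands. It limits the claim to a likely gain of uncertain size.

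A reader might draw three stronger conclusions that the documents do not support.

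- *That weeks 7 and 19 miss the scheduled draws.* They do not. With weeks counted from 0, the ends of weeks 7, 11 and 19 are D56, D84 and D140, all of them bDNA days. Table 1 labels the same visits W8, W12 and W20, so two numbering conventions are in use and naming study days would be clearer. No wrong visit is shown.
- *That the protocol itself rules out a single load.* Section 5.3.1 cites variability as the reason for at least three baseline loads; it does not say that one load is unusable. The screening loads also serve eligibility in section 5.1, through their average and their agreement with each other. The baseline rule supports averaging by analogy, but a single on-treatment value does not contradict it.
- *That the trial is underpowered and averaging is sure to bring it above 80%.* At the historical correlation of 0.83 the existing plan already has 90.6%. At r_s = 0.98 averaging reaches only 78.8%.

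**Conclusion.** The point holds as a missed gain in precision. One load per period enters the primary test, and a matched second load is collected and unused. With no dilution, averaging raises power for 1/3 log10 from 77% to between 79% and 97% at n = 20.

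That range assumes a same-period correlation between 0.98 and 0.75, equal cross-period correlations of 0.75, and a primary contrast between the on-treatment values of the two periods. The gain is safe against a 10% dilution if the same-period correlation is 0.90 or lower. At about 0.95 a 5% dilution uses it up, and above that averaging does worse than the current plan. It is a worthwhile, inexpensive improvement, with moderate confidence in its direction and little in its exact size.

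**What to change.** Before unblinding, amend section 7.0 as follows:

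- Define the primary endpoint as the within-patient difference between the mean log10 bDNA of D42 and D56 and the mean of D126 and D140, or the same contrast from a repeated-measures mixed model.
- If one of the two loads in a period is missing, use the available one.
- Keep D56 against D140 alone as a prespecified sensitivity analysis, which also shows whether the week-6 load dilutes the effect.
- State whether the endpoint is the on-treatment level or the change within each phase, as section 3.1 suggests. If it is the change, average the on-treatment value in the same way and recompute power for that endpoint.
- Name the visits by study day, so that the numbering in Table 2 and in Table 1 cannot be confused.

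The cost is wording only, with no new samples or visits. The one statistical cost is the possible dilution described above. If the investigators have reason to expect the effect to grow appreciably after week 6, they should say so and keep the single end-of-period value as primary.

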1.0 PRECIS

This protocol is a randomized, double blind, placebo controlled trial designed to study the effects of the lipid lowering statin, atorvastatin on HIV-1 viremia.

Untreated HIV-1 infection results in an incurable, progressive immunodeficiency and death, usually from opportunistic infections. Combination antiretroviral therapy (ARV) has been successful in suppressing HIV replication and reducing morbidity and mortality. [1] Long term ARV therapy is associated with the development of HIV-1 drug resistance, and significant adverse side effects including metabolic and cardiovascular complications. [2] Prolonged therapy with certain antiretrovirals is associated with increased risk of cardiovascular disease and a number of dyslipidemic syndromes, including increased levels of cholesterol, LDL, and triglycerides in peripheral blood. [3] New therapeutic strategies to suppress HIV-1 infection are essential.

Previously, in vitro studies suggested that exposure to cholesterol-lowering statins results in decreases in HIV-1 replication.[4, 5] The mechanisms of inhibition remain uncertain, but possibilities include disrupting membrane trafficking or cytoskeletal processes necessary for intracellular transport of viral proteins, or altering cellular activation state necessary for viral gene expression.[4-8] Initial in vivo studies of the effects of statins on HIV-1 have been largely anecdotal in nature and have yielded conflicting results. [9-12] Although statin therapy is commonly used in HIV-1 infection, adverse effects from the combination of antiretrovirals and statins are possible.[13] A more thorough understanding of the effects of statins on HIV-1 replication is essential to determine the potential therapeutic effect and to investigate the risks and benefits of this approach in vivo.

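### The primary paired test has no period term in a two-period crossover; adjusting for period costs almost nothing and protects power if viral load shifts between periods

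*Combined protocol and SAP*

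**What the plan says.** Section 7.0 assigns 22 patients to two sequences, 11 each, with two 8-week treatment periods separated by a 4-week washout. Viral load is evaluated at the end of each treatment period. For the primary comparison: "At the end of this study, the paired t-test will be used to test this hypothesis". If the data are clearly non-normal, "then the sign-rank Wilcoxon test will be used instead". Under the secondary objectives in the same section, comparisons of immune activation markers are "conducted by using the paired t-test if the measurements are continuous".

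The sample size uses the same test. The plan says "we estimate the standard deviation of the log₁₀ viral load as .74", and that "a correlation coefficient of 0.75 is used in our calculation". It gives 77% power with 20 subjects for a "1/3 log₁₀ drop in viral load with atorvastatin", and 90% and 98% for 0.4 and 0.5 log10.

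Section 7.0 discusses carry-over and assumes it negligible. It does not discuss a period effect. The linear mixed model mentioned with the secondary objectives is optional and additional, and no period term is named for it.

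**The concern.** In a two-period crossover, each patient's atorvastatin-placebo difference contains the treatment effect and, with a sign that depends on sequence, any general shift in viral load between the two periods. A paired test that pools the sequences cannot separate the two.

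- If the sequences have equal numbers, the shift cancels from the mean difference but stays in its standard error, so power falls.
- If the numbers differ, part of the shift remains in the estimate as bias.

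Randomising the sequence is what allows this shift to be removed, and the planned test does not use it.

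A shift is possible in this trial. The two evaluations, D56 and D140 in the schedule, are 84 days (12 weeks) apart. Section 5.3 allows vaccination at week 8, between the two periods, and extends the washout by 2 weeks because vaccination affects viral kinetics. With 77% planned power for 1/3 log10, there is little to give away.

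**Working it through.** **Inputs from Section 7.0.** SD of log10 viral load 0.74; correlation 0.75; 20 completers; type I error 0.05 (two-sided reproduces the plan's figure; sidedness is not stated); effect 1/3 log10.

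**Assumed.** Period shift p (period 2 minus period 1) of 0 to 0.3 log10. The documents give no value.

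**Step 1: reproduce the stated power.** SD of the difference = 0.74 × √(2 × (1 − 0.75)) = 0.523. Standard error = 0.5233/√20 = 0.117. Noncentrality = 0.3333/0.117 = 2.85 on 19 df. Exact power is 77.1%; at 0.4 and 0.5 log10 it is 90.0% and 98.2%. The plan's 77%, 90% and 98% are reproduced.

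**Step 2: what a period shift does.** Let τ be the true drop on atorvastatin. Placebo minus atorvastatin has mean τ + p in the atorvastatin-first sequence (n1 patients) and τ − p in the placebo-first sequence (n2 patients). Pooling n = n1 + n2 patients gives:

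- bias = p × (n1 − n2)/n;
- expected SD of the pooled differences = √(0.5233² + p² × 4·n1·n2/(n(n − 1))).

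For example, at 10:10 and p = 0.2: √(0.2738 + 0.04 × 400/380) = √0.3159 = 0.562.

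**Step 3: the period-adjusted test.** Take each patient's period difference, compare the sequences by a two-sample t-test, and halve the contrast; p cancels. SE = (0.5233/2) × √(1/n1 + 1/n2), with n − 2 df. At 10:10 the SE is again 0.117, now on 18 df. Power is 76.9%, 89.8% and 98.1% for 1/3, 0.4 and 0.5 log10, whatever p is. At 11:9 it is about 76.5% for 1/3 log10.

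**Step 4: balanced completers, 10:10, effect 1/3 log10.** Paired-t results under a shift are simulated, 200,000 runs per cell.

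| p | Expected SD | Paired-t power | Paired-t type I error | Adjusted power |
|---|---|---|---|---|
| 0 | 0.523 | 77% | 5.0% | 76.9% |
| 0.1 | 0.533 | 76% | 4.6% | 76.9% |
| 0.2 | 0.562 | 72% | 3.6% | 76.9% |
| 0.3 | 0.607 | 66% | 2.5% | 76.9% |

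The signed-rank fallback behaves similarly: 75% power at p = 0 and 63% at p = 0.3 (100,000 runs).

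**Step 5: 11:9 completers, effect 1/3 log10.** Bias is p × 2/20.

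| p | Absolute bias (log10) | Paired-t power, effect understated | Paired-t power, effect overstated | Adjusted power |
|---|---|---|---|---|
| 0.1 | 0.01 | 73% | 78% | 76.5% |
| 0.2 | 0.02 | 67% | 77% | 76.5% |
| 0.3 | 0.03 | 57% | 75% | 76.5% |

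If viral load is higher in period 2, the effect is understated when the placebo-first sequence is the larger and overstated when the atorvastatin-first sequence is.

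**Step 6: cost of adjusting when p = 0.** At 10:10, 77.11% − 76.86% = 0.25 points. At 11:9, 77.11% − 76.45% = 0.66 points.

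**The case against.** The best defence is that both harms need a non-zero p and the documents supply none. This stands. The values 0.2 and 0.3 are 60% and 90% of the effect sought, and at p = 0.1 the balanced loss is about one point. A reader might infer that drift is to be expected because "Untreated HIV-1 infection results in an incurable, progressive immunodeficiency and death". That sentence concerns immunodeficiency and death without treatment, not viral-load change over 12 weeks. Section 5.1 also selects for stability: no acute infection, CD4 above 350, at least three months off antiretrovirals, and three baseline viral loads close to one another. The washout extension after vaccination is itself meant to limit that source.

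Second, imbalance is limited. Section 5.3.2 fixes 11 per sequence, and Section 5.4 replaces discontinued patients according to the prior randomisation. A reader might test the plan at a split such as 8:12, but this scheme does not lead to 12 completers in one sequence. With 20 completers the most uneven split is 11:9. Some imbalance remains possible, because loss to follow-up is not expressly among the reasons that trigger replacement. Replacement also does nothing for the balanced-case power loss.

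Third, Section 3.1 frames the objective as changes within each phase. If those changes were tested, a linear drift would cancel, since both periods last 8 weeks. Section 7.0, however, describes evaluation at the end of each period.

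Fourth, a reader might infer that the primary test is invalid or that the signed-rank test loses its symmetry in general. Neither follows. Total type I error did not rise above the nominal level because of a period shift in any scenario tried; with unequal sequences the rejections move towards one tail (11:9, p = 0.3: about 2.3% and 0.65%). With equal sequences the pooled null distribution is still symmetric about zero. Symmetry fails only when the sequences are unequal.

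**Conclusion.** The point holds as a cheap improvement that should be made. The primary test, its fallback and the paired t-tests for continuous markers ignore period in a design randomised so that period can be removed.

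If p is 0.1 to 0.3 log10, the balanced paired t-test loses about 1 to 11 points of its 77% power and becomes conservative. At 11:9 the bias is 0.01 to 0.03 log10, at most 9% of the target (0.03/0.333). Power at p = 0.3 is then 57% or 75%, depending on which sequence loses patients.

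These sizes rest on an assumed p, the plan's SD and correlation, end-of-period values as the outcome, and negligible carry-over as the plan assumes. If p is zero, the planned test is valid and very slightly more powerful. The documents do not support calling drift expected or the type I error inflated.

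**What to change.** In Section 7.0, make the primary test a two-sample t-test between sequences on the within-patient period differences, with the contrast halved. For patients with both periods this is equivalent to a mixed model with treatment, period and sequence as fixed effects and patient as random. For clearly non-normal data, use a Wilcoxon rank-sum test between sequences on the same period differences, with a Hodges-Lehmann interval. Apply the same model to the continuous secondary markers.

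The cost is a short change of text and one degree of freedom (19 to 18 with 20 completers). If there is no period effect, the loss is 0.25 points of power at 10:10 and 0.66 points at 11:9. The sample size does not change, and the stated 77%, 90% and 98% remain right to the whole percent at 10:10.
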